### 3 List of Abbreviations and Definitions

AE	Adverse Event
CI	Chief Investigator
COPD	Chronic Obstructive Pulmonary Disease
CRF	Case Record File
ICF	Informed Consent Form
NHS R&D	National Health Service Research & Development
NRD	Neural Respiratory Drive
NIV	Non-invasive ventilation
PI	Principle Investigator
QA	Quality Assurance
QC	Quality Control
Participant	An individual who takes part in a clinical trial
REC	Research Ethics Committee
RMS	Root Mean Square
SAE	Serious Adverse Event

#### **Glossary of Definitions and Terms**

**AECOPD:** Acute Exacerbation of Chronic Obstructive Pulmonary Disease is a clinical diagnosis made when a patient with COPD experiences a sustained (e.g. 24–48 h) increase in cough, sputum production, and/or dyspnoea.

**(M)EWS:** (Modified) Early Warning Score is a guide used by medical services to quickly determine the degree of illness of a patient. It is based on data derived from four physiological readings (systolic blood pressure, heart rate, respiratory rate, body temperature) and one observation (level of consciousness, AVPU).

**EMG:** Electromyography is a diagnostic procedure to assess the health of muscles and the nerve cells that control them (motor neurons).

**EMGdi%max:** Peak inspiratory Root Mean Square EMG normalized to the sniff manoeuvre is a measurement found of the Neural Respiratory Drive using diaphragmatic EMG.

**EMGpara%max:** Peak inspiratory Root Mean Square EMG normalized to the sniff manoeuvre is a measurement found of the Neural Respiratory drive using parasternal muscle EMG.

**FEV1:** Forced Expiratory Volume in one second – the volume of air exhaled in the first second of the **FVC** (Forced Vital Capacity) manoeuvre and is the most reproducible measurement of airway obstruction.

**IC:** Inspiratory Capacity – the volume of air that can be inspired after tidal expiration.

**Myotrace device:** Measures parasternal EMG signal by means of electrode leads and differential amplification, respiratory signal by means of a nasal cannula and an additional differential pressure sensor and acceleration signal by means of a 3D-accelerometer.

**NIV:** Non Invasive Ventilation is ventilator support that is not invasive, thus no endotracheal tube or tracheostomy tube is needed to ventilate the patient.

**NRD:** Neural Respiratory Drive is a measure derived from the electrical activation of the respiratory muscles that is often measured by diaphragmatic EMG. NRD is an indirect measure of the balance between the load placed on the respiratory muscle pump and the capacity of the respiratory muscle pump.

**PAP:** Positive Airway Pressure

## 4 Summary/Synopsis

Title	Pilot feasibility study to determine the clinical effectiveness of neural respiratory drive (NRD) to predict COPD exacerbations at home
Protocol Short Title/Acronym	NRD to predict COPD exacerbations at home
Protocol Version number and Date	Version 1.6 4 th September 2017
Study Phase if not mentioned in title	Pilot study
IRAS Number	232381
REC Reference	
Study Duration	12 months
Sponsor name	Guy's & St Thomas' NHS Foundation Trust
Chief Investigator	[name]
Funder	National Institute for Health Research Biomedical Research Centre at Guy's and St Thomas' NHS Foundation Trust. Equipment (NRD measurement equipment and physical activity monitors) provided by Philips and Affiliates.
Medical condition or disease under investigation	Chronic Obstructive Pulmonary Disease
Purpose of research	To identify whether NRD measurements at home following admission to hospital with exacerbation of COPD can detect an exacerbation within 30 days of discharge.
Primary objective	To investigate whether home measurement of NRD can detect a re-exacerbation of COPD within a 30-day post hospital discharge period.
Secondary objective (s)	
Clinical:
 
To validate NRD as an advanced physiological biomarker of clinical respiratory deterioration and re-exacerbation of COPD.
 
To analyse NRD trajectory as it relates to standardly subjective measurements of respiratory symptoms e.g. COPD Assessment Test or the EXACT-PRO questionnaire.
 
To determine positive and negative predictive value of NRD to predict re-exacerbation of COPD.
 
To investigate composite clinical features to detect re-exacerbation of COPD
 
To assess correlation of change in NRD, physical activity and symptom resolution.
 
Feasibility:
 
To investigate quality of the parasternal EMG measurements.
 
Technical:
 
To use the data collected during the study to tune, refine, optimise the automated NRD calculation algorithm.

Number of Subjects/Patients	30
Study Type	Observational pilot feasibility study
Endpoints	
Primary end-point:
 
Change in NRD from baseline to day prior to an acute exacerbation of COPD.
 
Secondary end-points:
 
Change in NRD from peak exacerbation (hospital) to recovery baseline (home)
 
Correlation of time to recovery as measured by NRD and EXACT-PRO

	
Correlation of NRD, EXACT-PRO and daytime activity from hospital discharge to recovery
 
Physician-assessed exacerbation within 30-day post-discharge
 
Self-treated exacerbation within 30-day post-discharge
 
All cause hospital readmission within 30-day post-discharge
 
Mortality within 30-day post-discharge
 
Recovery as defined by the EXACT-PRO within 30-day post-discharge
 
Medication change within 30-day post-discharge
 
Unplanned healthcare contacts
 
Attendance of emergency department (without admission)

Main Inclusion Criteria	
Age 40-80 years
 
Patients hospitalized with a primary diagnosis of an acute exacerbation of COPD
 
Body mass index (BMI) <math>\leq 35 \text{ kg/m}^2</math>
 
Cognitively and linguistically able to follow instructions given in English and provide informed consent
 
To be discharged to home following the hospitalization
 
Patient lives in the catchment area served by the Lane Fox Unit at Guy's and St Thomas' NHS Foundation Trust in a home environment deemed safe by the investigators to perform home assessments

Statistical Methodology and Analysis	NRD measurements will be analysed after assessments to obtain EMG data. Independent or paired t-test and ANOVA for normally distributed data, non-parametric tests for non-normally distributed data. Measures of association between the defined indices of NRD, the monitored endpoints and routinely used metrics. Univariate and multivariate logistic regression may be used to evaluate predictive value of investigated features using Receiver operating Characteristic Methodology.
Human Tissue Samples (if applicable)	
Results of arterial and venous blood tests taken as part of routine clinical care will be recorded:
 
 
• Arterial blood gas
 
• Venous blood tests: haemoglobin, white cell count including differential, platelet count, urea, creatinine, C-reactive protein
 

Data collected/storage (if applicable)	
Patient data will be de-identified.
 
 
• All de-identified data will be stored on a password-protected computer stored in a locked seminar room on the Lane Fox Respiratory Unit, St Thomas' Hospital.
 
• All trial data will be stored in line with the Medicines for Human Use (Clinical Trials) Amended Regulations 2006 and the Data Protection Act and archived in line with the Medicines for Human Use (Clinical Trials) Amended Regulations 2006 as defined in the Kings Health Partners Clinical Trials Office Archiving SOP.
 

## 5 Introduction

Chronic obstructive pulmonary disease (COPD) is the fifth biggest cause of death in the United Kingdom (UK) and second most common cause of hospital admissions. The UK population prevalence is 1.5% (5.1% in the United States of America, USA). As per the UK Office for National Statistics, COPD was the underlying cause of death in 30,858 cases in England and Wales in 2015. The direct cost of treating COPD is £1.9 billion annually. Innovative improvements in healthcare delivery, including strategies to prevent hospital readmission are essential.

In the USA, across a selection of 15 states in 2008, there were 190,700 index admissions with a principal diagnosis of COPD. The 30-day readmission rate for an acute exacerbation of COPD (AECOPD) was 7.1% and the rate of 30-day readmissions for other primary diagnoses but with COPD as an additional diagnosis was 17.3 percent. Indeed, these data indicate that COPD accounts indirectly and directly for one out of five readmissions to hospital within 30 days. Healthcare costs were consistently higher for readmissions than for initial stays. Cost for the 30-day readmission, with COPD as principal diagnosis, was 18% higher than for the index stay. Costs were more than 50% greater for the readmission with COPD as any diagnosis or for all-cause readmissions. Currently in the UK, several European countries and the USA, healthcare providers and institutions face financial penalties for patients who are readmitted within 30 days. The additional healthcare costs could be reduced by innovative approaches directed to reduce hospital readmission.

Monitoring the trajectory of recovery is essential for COPD patients recovering from an exacerbation and potentially this will determine the need for escalation of care as well as the requirement for delayed or supported discharge at the end of their hospital stay. Physiological deterioration leading to critical care admission often goes undetected and early identification by measuring advanced physiological biomarkers, such as neural respiratory drive (NRD), could improve outcome as well as reduce health care costs by reducing late intervention and admissions to hospital and critical care. Early detection of treatment failure is recommended by the Royal College of Physicians of the UK and the National Institute for Health and Clinical Excellence (NICE). Early warning scores (EWS) have therefore been developed in the UK using standard physiological variables to derive an aggregate score. Higher scores are associated with worse outcomes. However the scores are not always employed and their effectiveness, particularly in the COPD cohort, is controversial.

NRD, or drive to breathe, directly reflects the balance between respiratory muscle load and respiratory muscle capacity. Diaphragmatic electromyography (EMG), performed using an array of electrodes inserted into the oesophagus, has been demonstrated to be a robust technique for assessing NRD. The magnitude of the EMG signal is expressed as the root mean square (RMS) of the EMG voltage trace. The NRD is then derived from the RMS of the diaphragmatic EMG signal expressed as a percentage of the maximal EMG (EMGdi%max). However, this technique is of limited use in the acutely unwell COPD patient, as it required the insertion of an oesophageal multi-pair electrode catheter.

Second intercostal space parasternal EMG, acquired using electrodes placed on the chest wall on either side of the sternum, avoids this technical difficulty. The parasternal muscles are obligate muscles of respiration with minimal post-inspiratory activity. Furthermore, the parasternal muscles make a relatively greater contribution to ventilation during periods of increased hyperinflation, such as during an acute exacerbation of COPD (AECOPD), as the resting length of the parasternal muscles is less affected than diaphragm^21. The activity of these muscles would be expected to be high at the beginning of an AECOPD and decrease with subsequent unloading of the parasternal muscles through treatment with bronchodilators, corticosteroids and antibiotics.

In a pilot feasibility study of this technique, Murphy *et. al.* demonstrated that the change in NRD during hospital admission was a marker of physician-defined clinical deterioration and, furthermore,

change in NRD from admission to discharge identified patients with COPD who were readmitted within 14 days. This study was in a small group of selected patients with AECOPD, with the majority of patients having only a single pair of NRD measurements made during their hospital admission. The NRD was derived from the RMS of the parasternal EMG expressed as a percentage of maximal parasternal EMG obtained during a sniff manoeuvre ( $EMG_{para\%max}$ ). An additional clinically useful measure was the NRD index (NRDI), which was calculated as the product of  $EMG_{para\%max}$  and respiratory rate.

A subsequent study from the same group by Suh *et. al.* at a UK teaching hospital enrolled patients with a physician diagnosis of AECOPD within 12 hours of admission. Spirometry, inspiratory capacity (IC),  $EMG_{para}$ , routine physiological parameters, MEWS, modified Borg scale for dyspnoea and physician defined episodes of deterioration were recorded daily until discharge. Readmissions at 14 and 28 days post discharge were also recorded. 120 patients were recruited (age  $70\pm9$  years, forced expiratory volume in 1s (FEV1) of  $30.5\pm11.2$  as percentage of predicted). Subjective worsening of dyspnoea, defined as at least one-point increase in Borg scale, was associated with increases in  $EMG_{para\%max}$  and MEWS, whereas physician-defined inpatient clinical deterioration was associated with an increase in  $EMG_{para\%max}$  alone. Admission-to-discharge change ( $\Delta$ ) in the normalized value of  $EMG_{para}$  ( $\Delta EMG_{para\%max}$ ) was inversely correlated with  $\Delta FEV_1$  ( $r=-0.38$ ,  $p<0.001$ ) and  $\Delta IC$  ( $r=-0.44$ ,  $p<0.001$ ).  $\Delta EMG_{para\%max}$  predicted 14-day readmission (OR 1.13, 95% 1.03 to 1.23) in the whole cohort and 28-day readmission in patients under 85 years (OR 1.09, 95% CI 1.01 to 1.18)

Two further studies were conducted to ascertain if participants could perform self-measurement of NRD following training by a nurse coordinator. This study enrolled 10 healthy controls and 10 stable COPD patients attending outpatient clinic and performing self-measurement steps to obtain NRD measurements over two visits. The second study was conducted with 10 stable COPD participants who self-measured NRD in their home for 7 consecutive days. The measurement steps for both studies were the same as the ones performed during the UK studies, including skin preparation, placement of two electrodes at the 2nd intercostal space and one ground electrode on the clavicle, positioning of nasal cannula and breathing at rest for 6 minutes, followed by a sniff manoeuvre. For both of these studies, equipment measuring parasternal EMG signal using electrode leads and differential amplification (termed Myotrace device), respiratory signal using nasal cannulae and a differential pressure sensor, and acceleration signal by means of an accelerometer was used. The data acquisition system (Porti7 from the company TMSi) was powered by a medical grade external power supply. The acquired data were sent to a notebook via optical fibre, where the signals could be further processed, stored, and visualized.

The results from the first study indicated that most participants could perform self-measurement using the Myotrace device after being trained by a coordinator and following picture instructions. The second study demonstrated that:

- The measure was acceptable to patients. When interviewed at the end of the study, 9 out of 10 found the measurement easy to very easy to perform. All felt confident to very confident to perform the measurement, and 8 felt that they would be likely to very likely to conduct the measurement at home, 6 of those for one month.
- All 10 patients managed the different measurement steps (skin preparation, electrode placement, nasal cannula placement). Although not perceived by the patients as the most difficult step, it was observed during the measurements that adopting a consistent and relaxed posture and behaviour during breathing at rest could represent a challenge for some patients.
- The majority of the 10 patients (7/10) could perform self-measurements with acceptable reproducibility and accuracy, as assessed by inter-occasion reliability and inter-observer reliability (note that in that study the coordinator also performed a measurement every day, which allowed to compare measurements between the coordinator and each patient). Some

promising directions for improvement were also identified at different levels (algorithm, form factor, user experience and instructions for use).

Overall, further data (larger sample size and higher COPD severity) are required to validate the level of reproducibility of the NRD measurement, also in conjunction with the ability to detect clinically relevant change in NRD due to deterioration in the home.

This study will be a single arm, pilot feasibility prospective observational study to assess whether NRD when utilized as an objective monitoring signal, is able to detect a clinical respiratory deterioration (re-exacerbations or failure to respond to treatment) in COPD patients within 30 days of discharge from hospital, following index hospitalization for AECOPD. The goal of using this advanced physiological biomarker is to facilitate early intervention and prevent hospital readmission and/or reduce the impact of relapse. As a pilot feasibility study, the aims are to assess the practical limitations to acquiring NRD in the home setting. Furthermore, data will be collected to assess the potential for NRD to detect and predict re-exacerbations allowing potential sensitivity and specificity to be calculated. If this pilot study confirms that NRD measurements are practical to acquire at home and successfully detect and predict future exacerbations of COPD, this will facilitate a study to validate the use of the Myotrace device by patients themselves in detecting and predicting AECOPD at home following index hospitalization for AECOPD.

Physical activity is a key feature of stable and acute COPD, with inactivity being associated with poorer outcomes including reduced health related quality of life scores, hospital admissions and increased mortality. This study will include a quantification of physical activity using wrist-worn physical activity monitors, which will be compared to NRD measurements. Using an accelerometer, the physical activity monitor will collect data on total sleep time, time spent awake after sleep onset, sleep onset latency, sleep efficiency, average activity (counts/minute), maximum activity (counts/minute), mobile time, average mobile bout, immobile time and total wake and sleep times. In this way, physical activity will be evaluated as an additional advanced physiological biomarker to identify further re-exacerbations of COPD and predict readmission.

COPD exacerbations will be pre-defined according to the following criteria in a hierarchical fashion.

- COPD-related hospital admission - worsening respiratory symptoms (cough, wheeze, increased sputum production, increased volume of sputum and/or increased breathlessness) with senior physician (registrar or consultant) assessment and treatment for acute COPD exacerbation started on admission to hospital.
- Physician-assessed exacerbation - worsening respiratory symptoms (cough, wheeze, increased sputum production, increased volume of sputum and/or increased breathlessness) with physician assessment and COPD treatment escalated (increased beta-agonist use as inhaled or nebulized therapy and/or oral corticosteroids and/or oral antibiotics) by physician WITHOUT admission to hospital.
- Self-treated exacerbation - worsening respiratory symptoms (cough, wheeze, increased sputum production, increased volume of sputum and/or increased breathlessness) WITHOUT physician assessment but patient self-initiated AECOPD treatment (use of rescue pack of oral corticosteroids and/or oral antibiotics, depending on standard of care at clinical site).

Exacerbations will also be categorized by according to the GOLD definition:

- Mild (treated with short acting bronchodilators only, SABDs)
- Moderate (treated with SABDs plus antibiotics and/or oral corticosteroids) or
- Severe (patient requires hospitalization or visits the emergency room). Severe exacerbations may also be associated with acute respiratory failure.

Note that the EXACT questionnaire will be used throughout the study in an attempt to monitor symptom-based changes in patient status. The EXAcerbations of Chronic Pulmonary Disease Tool is a Patient-Reported Outcome measure (EXACT-PRO) designed to standardize the method for evaluating the frequency, severity and duration of both reported and unreported AECOPD in studies. The EXACT-PRO total score is computed across the 14 items and has a theoretical range of 0 to 100, with higher values indicating a more severe condition. Specifically, changes in the total score may be used to define recovery from the primary exacerbation event.

## 6 Trial objectives and purpose

### **Primary objective:**

To investigate whether home measurement of NRD can detect a re-exacerbation of COPD (symptom based definition) within a 30-day post hospital discharge period.

### **Secondary objectives:**

#### **Clinical:**

- To validate NRD as an advanced physiological biomarker of clinical respiratory deterioration and re-exacerbation of COPD.
- To analyse NRD trajectory as it relates to standardly subjective measurements of respiratory symptoms e.g. COPD Assessment Test or the EXACT-PRO questionnaire.
- To determine positive and negative predictive value of NRD to predict re-exacerbation of COPD.
- To investigate composite clinical features to detect re-exacerbation of COPD.
- To assess correlation of change in NRD, physical activity and symptom resolution.

#### **Feasibility:**

- To investigate quality of parasternal EMG measurements performed in the home environment

#### **Technical:**

- To use the data collected during the study to tune, refine, optimise the automated NRD calculation algorithm

## 7 Study design & Flowchart

### 7.1 Study Design

#### **Primary end-point:**

Change in NRD from baseline to day prior to an acute exacerbation of COPD.

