#### **Secondary end-points:**

Change in NRD from peak exacerbation (hospital) to recovery baseline (home)

Correlation of time to recovery as measured by NRD and EXACT-PRO

Correlation of NRD, EXACT-PRO and daytime activity from hospital discharge to recovery

Physician-assessed exacerbation within 30-day post-discharge

Self-treated exacerbation within 30-day post-discharge

All cause hospital readmission within 30-day post-discharge

Mortality within 30-day post-discharge

Recovery as defined by the EXACT-PRO within 30-day post-discharge

Medication change within 30-day post-discharge

Unplanned healthcare contacts

Attendance of emergency department (without admission)

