### **14.2 Statistical analysis**

For all analyses,  $p<0.05$  will be deemed statistically significant. Comparison of data with one or more factors will be analysed using independent or paired t-test and ANOVA with repeated measures (if needed) for normally distributed data, and non-parametric tests in cases of non-normally distributed data, whenever applicable. Measures of association between the defined indices of NRD, the monitored endpoints and routinely used metrics will be investigated (e.g. using regression analysis). At last, univariate and multi-variate logistic regression may be employed to evaluate the predictive value of a number of investigated features (using the Receiver Operating Characteristic Methodology).

Interim analysis will be performed after 5 patients have been readmitted.

[name] (King's College London) will be involved in statistical analysis for the study. The Lane Fox Research Unit has an existing contract with [name] for *ad hoc* statistical support.

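### The primary endpoint has a value only in participants who re-exacerbate and leaves its baseline unresolved, so by itself it cannot show whether home NRD detects re-exacerbation

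*Protocol*

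**What the plan says.** The primary endpoint, in section 7.1 and in the synopsis, is "Change in NRD from baseline to day prior to an acute exacerbation of COPD". No comparison day or value is given for participants without an exacerbation. The primary objective in section 6 concerns detection: "To investigate whether home measurement of NRD can detect a re-exacerbation of COPD (symptom based definition", within 30 days of discharge.

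Participants who stay well enter elsewhere:
- Section 6, secondary objective: "To determine positive and negative predictive value of NRD to predict re-exacerbation of COPD".
- Section 14.2, a firm plan: "Measures of association between the defined indices of NRD, the monitored endpoints and routinely used metrics will be investigated". The tests listed there include the independent as well as the paired t-test.
- Section 14.2, an option: "univariate and multi-variate logistic regression may be employed to evaluate the predictive value of a number of investigated features", using ROC methodology.
- Section 5: sensitivity and specificity are mentioned as something the data should allow.

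The endpoint does not say what baseline means. In sections 9.3, 9.5 and 13.1 the baseline assessment is the first study assessment in hospital, and section 8 has patients enrolled within 16 hours of admission. A secondary endpoint in section 7.1 uses the word for a later state: "Change in NRD from peak exacerbation (hospital) to recovery baseline (home". On recovery, section 5 says only that "changes in the total score may be used to define recovery from the primary exacerbation event". NRD is also measured on the day of discharge (sections 9.3, 9.4, 13.1).

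**The concern.** Detection means telling participants who are about to relapse from those who are not. A mean change observed only in relapsers carries no information on what NRD did over the same days in everyone else. It cannot yield specificity, predictive values or a ROC area. This is a gap in what the endpoint measures and would remain at any sample size.

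The open baseline adds a second difficulty. Section 5 expects parasternal activity to be high when an exacerbation starts and to fall with treatment. A change counted from the admission reading therefore includes the treatment response, whereas a change counted from a recovered home reading does not. A recovery baseline may also be missing for some relapsers: section 5 counts "re-exacerbations or failure to respond to treatment" as deterioration to be detected, and section 7.1 treats EXACT-PRO recovery within 30 days as an outcome, not as a given.

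Sections 5 and 14.1 make this pilot the basis for a later validation study and its sample size. A headline result with no comparator and an unclear reference reading serves neither purpose well.

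**Working it through.** **There is no plan figure to reproduce.** Section 14.1 sets 30 completers without a power calculation and gives no effect size or SD.

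**1. How many participants have a primary endpoint value**

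Inputs: N = 30 (section 14.1) and a 20% readmission rate in this population (section 11; the time unit is missing after 28 and is read as days). The rate is a lower-end proxy, because section 5 also counts physician-assessed and self-treated events without admission. Section 5 quotes 7.1% from US data, which would give 30 × 0.071 = 2.1. The rate of all re-exacerbations is not given, so 40% and 50% are assumptions.

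- Binomial(30, 0.20): mean 30 × 0.20 = 6; central 95% range 2 to 11; P(3 or fewer) = 0.12.
- 30 × 0.40 = 12; 30 × 0.50 = 15.

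**2. What a relapser-only result can tell**

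Assume that the change in relapsers is Normal(+1, 1) in SD units and that in non-relapsers is Normal(m, 1). The ROC area is Φ((1 − m)/√2). At a cut-off of +0.5 SD, sensitivity is 1 − Φ(0.5 − 1) = 69% throughout, and specificity is Φ(0.5 − m).

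| Mean change in non-relapsers, m | ROC area | Specificity |
|---|---|---|
| −1 | 0.92 | 93% |
| 0 | 0.76 | 69% |
| +1 | 0.50 | 31% |

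The primary endpoint is the same in all three rows.

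**3. What the choice of baseline does**

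Let the admission reading be A, the fall to discharge D and the pre-relapse rise R. Suppose there is no trend after discharge. The reading before relapse is then A − D + R.

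- From admission: (A − D + R) − A = R − D.
- From discharge, or from a home reading equal to it: (A − D + R) − (A − D) = R.

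The two differ by D, and the sign differs whenever 0 < R < D. With a post-discharge trend T up to the reading before relapse, the changes from admission and from discharge are T + R − D and T + R. The gap remains D, but whether the signs differ then depends on T as well.

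**4. Precision of a relapser-only mean and of a contrast with non-relapsers**

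Expected 95% CI half-widths in SDs of the change, from simple t intervals: t(0.975, n − 1)/√n for the relapser-only mean, and t(0.975, 28) × √(1/n + 1/(30 − n)) for the contrast.

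| Relapsers v others | Relapser-only mean | Contrast |
|---|---|---|
| 6 v 24 | 2.571/√6 = 1.05 | 2.048 × 0.456 = 0.94 |
| 12 v 18 | 2.201/√12 = 0.64 | 2.048 × 0.373 = 0.76 |
| 15 v 15 | 2.145/√15 = 0.55 | 2.048 × 0.365 = 0.75 |

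For a ROC area of 0.76 (an assumed 1 SD separation), the Hanley-McNeil standard errors are 0.123, 0.094 and 0.089. The logit-scale 95% CIs are 0.46 to 0.92, 0.54 to 0.90 and 0.55 to 0.89.

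**The case against.** The best defence is that the comparison exists elsewhere in the plan. Section 14.2 commits to relating NRD to the monitored endpoints, which in section 7.1 include physician-assessed and self-treated exacerbation and readmission. That requires participants who stay well. A two-group t-test is listed, and predictive values are an objective. In an unpowered pilot, a within-person change before the event is a defensible early signal. The unqualified word baseline also matches the headings in sections 9.3 and 13.1, and an analysis plan that is not shown may fix the exact reading.

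Much of this stands, and it limits the point to the primary endpoint taken by itself. A reader might infer that the study cannot assess detection at all. The protocol does not support that, because NRD is collected in everyone and some planned analyses can address the question. But none of them is tied to the primary endpoint, and the ROC analysis is optional. Pilot status excuses the absent power calculation, not a mismatch between objective and endpoint. The two uses of baseline are in the protocol itself.

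A reader might also infer that a trend shared by all participants would often pass for a pre-relapse rise. The only direction the protocol supports is a fall with treatment. Under an assumed shared fall of 0.5 SD and no pre-relapse signal, a paired test would show a significant rise in 0.14%, 0.02% and 0.01% of studies with 6, 12 and 15 relapsers. A shared fall would mask a signal rather than mimic one.

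The objection that a contrast with non-relapsers has its own assumptions and costs is fair; these are set out with the fix.

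**Conclusion.** The point holds and should be fixed. The primary endpoint exists only after a re-exacerbation, the primary objective is detection, and the endpoint alone is compatible with a ROC area anywhere from 0.50 to 0.92 in the cases worked above. About 6 of 30 participants would contribute at the 20% proxy, or 12 to 15 at an assumed 40 to 50%. The logical gap does not depend on that rate; the ROC figures rest on assumed normal changes with equal SD.

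The baseline is unresolved between the first inpatient assessment and a recovered home state. The size of the change depends on that choice. A sign reversal is possible but conditional: the simple R − D against R comparison assumes no post-discharge trend. It would also go too far to say that some relapsers will lack a recovery baseline. The protocol shows only that they may.

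**What to change.** In section 7.1 and the synopsis:

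1. Name one reference NRD reading available for every participant, for example the pre-discharge reading, and call the first inpatient reading admission NRD.
2. Make the primary comparison the change from that reference to the last home reading before onset in relapsers, against the change over the same time since discharge in participants still exacerbation-free, with a 95% CI.
3. Report the ROC area for that change as a pilot estimate. Keep the within-relapser change as a supporting description.

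The matching or modelling method and the handling of very early relapse can go to the SAP.

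The cost is wording; no visits or NRD measurements are added. The protocol should state these limits:
- The contrast isolates a pre-relapse rise only if the post-discharge trend is otherwise common to both groups. The earlier inpatient study described in section 5, where the admission-to-discharge change predicted readmission, suggests that trajectories up to discharge may already differ.
- NRD may not be fully recovered at discharge.
- Section 9.3 specifies readings before and after the short-acting bronchodilator only for the hospital stay, so matching that state at home may not be possible.
- Home-visit frequency is not stated, so matched days may need a window.
- With 12 or 15 relapsers the contrast is less precise than the relapser-only mean (half-width 0.76 v 0.64 and 0.75 v 0.55 SD). With no shared trend and an assumed 1 SD rise, simple t-tests have power 74% v 88% and 75% v 95%; with 6 relapsers, 56% v 51%. Power for a matched or mixed-model analysis was not computed.
- The number of relapsers does not change, so the ROC area stays imprecise.
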